2.3 Endpoint Analysis

2.3.1 Primary Endpoint(s)

The primary analysis population is the Intent-to-treat (ITT) population. The primary endpoints of SLDA rate at 30 days and APS at discharge will be summarized with patient counts and percentages/rates, and exact 95% Clopper-Pearson confidence intervals as described in Section 2.2. Registered patients who do not have MitraClip procedure attempted will be excluded from the ITT population.

2.3.2 Other Endpoints

The analyses for the other endpoints will be performed using the methods described in Section 2.2 for the ITT population.

2.4 Interim Analysis

No formal interim analyses are planned for this study. As such, no formal statistical rule for early termination of the trial is defined. Interim study reports with descriptive analysis may be produced for regulatory or reimbursement purposes.

2.5 Timing of Analysis

Analyses for the primary endpoints will be performed when the last registered patient completes 30-day follow-up. Annual progress reports (up to 3 years) will be submitted to the regulatory authority at each time point accordingly.

Data will be collected at the following time points:

- Baseline (pre-procedure)
- Procedure
- Discharge
- 30 days (30 days±14 days) (by visit)
- 1 year (365 days±28 days) (by visit)
- 2 years (730 days±28 days) (by visit)

Statistical Analysis Plan

- 3 years (1095 days \pm 28 days) (by visit)

2.6 Handling of Missing Data

All analyses will be based on available data. Missing data will not be imputed. Any unused or spurious data will be documented as appropriate in the final report. For the primary endpoint of APS, a 30-day echocardiogram will be used if discharge echocardiogram is unavailable or uninterpretable.

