5. INFORMATION TO BE COLLECTED FOR THE SURVEILLANCE

5.1 Baseline

1) **Basic Patient Information**

- Registration date
- Date of birth or age at procedure
- Gender
- Height
- Weight

2) **Cardiac Status at Registration**

- Mitral regurgitation severity and etiology, as reported by site
 - Functional mitral regurgitation (FMR)
 - Degenerative mitral regurgitation (DMR)
- Ischemic status at registration, especially previous interventions
- New York Heart Association (NYHA) functional class
- Atrial fibrillation: paroxysmal, persistent, permanent
- Previous cardiac resynchronization therapy
- Previous percutaneous coronary intervention (PCI) and coronary artery bypass grafting (CABG)
- Previous heart valve surgery or other cardiothoracic surgeries
- Left ventricular function and anatomy as reported by site
 - Left ventricular ejection fraction (LVEF)
 - Left ventricular end systolic volume (LVESV), left ventricular end diastolic volume (LVEDV), left ventricular end systolic dimension (LVESD), left ventricular end diastolic dimension (LVEDD).

3) **Risk Factors and Medical History**

- General heart disease risk factors
 - Smoking status
 - Diabetes
 - Hypertension
 - Dyslipidemia
- Renal failure
 - Currently on dialysis
- Previous cerebrovascular accident (CVA)/ transient ischemic attack (TIA)
- Previous peripheral disease and intervention
- Chronic pulmonary disease
- Previous major bleeding
- Cirrhosis
- Cancer

- Subject is deemed difficult for mitral valve surgery due to either STS surgical mortality risk for mitral valve replacement of $\geq 8\%$ OR due to the presence of one of the following risk factors:
 - Porcelain aorta or mobile ascending aortic atheroma
 - Post-radiation mediastinum
 - Previous mediastinitis
 - Functional MR with LVEF $<40\%$
 - Over 75 years old with LVEF $<40\%$
 - Re-operation with patent grafts
 - Two or more prior cardiothoracic surgeries
 - Hepatic cirrhosis
 - Other surgical risk factor(s)

4) Classes of Cardiovascular and Heart Failure Medications

- Angiotensin converting enzyme (ACE) inhibitor
- Angiotensin II receptor blocker
- Aldosterone receptor blocker
- Beta-blocker
- Diuretics
- Calcium channel blocker
- Anti-Platelets
- Anticoagulants
- Antiarrhythmics
- Cardiac glycosis (Digitalis)
- Statins
- Other vasodilators
- Other cardiac medication

5) Transthoracic and Transesophageal Echocardiography

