6.2 Other Endpoints

Other endpoints will be evaluated at the specific follow-up timepoints per typical mitral regurgitation intervention clinical studies, including but not limited to, mitral regurgitation severity score, NYHA class, LV function and anatomy, cardiac medication, adverse events, device deficiency. Rate of heart failure hospitalizations in the 1 year post-procedure will be compared to the 1 year prior to the index procedure.

7. Statistical Analysis

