1.4.2 Other Endpoint(s)

Other endpoints will be evaluated at the specific follow-up time points may include, but not limited to, mitral regurgitation severity, New York Heart Association (NYHA) class, LV function and anatomy, cardiac medication, adverse events and device deficiency. Rate of heart failure hospitalizations in the 1-year post-procedure will be compared to the 1 year period prior to the index procedure.

Statistical Analysis Plan

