2.2.1 Descriptive Statistics for Continuous Variables

For continuous variables, such as age, results will be summarized as number of observations, means and standard deviations, and where applicable, with quartiles, minimums, maximums, and 95% confidence intervals for the means. Differences between the two groups, where specified, will be summarized with the differences of the two means, and 95% confidence intervals for the difference between the means.

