2.2.2 Descriptive Statistics for Categorical Variables

For binary variables (e.g. SLDA rate, gender, diabetic status, etc.), results will be summarized with patient counts and percentages/rates, and where applicable, with exact 95% Clopper-Pearson confidence intervals. Differences between the two groups, when specified, will be summarized with the difference in percent and the Newcombe³ score 95% confidence interval for the difference of two percentages.

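### NYHA class, LV measures and MR grade to 3 years are summarised on available data, with no same-patient change and no category for death, so selective loss of sicker patients can pass for improvement or durability

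*SAP*

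**What the plan says.** SAP 1.4.2 lists the other endpoints as "mitral regurgitation severity, New York Heart Association (NYHA) class, LV function and anatomy, cardiac medication, adverse events and device deficiency". Protocol 6.2 frames them in the same way: "Other endpoints will be evaluated at the specific follow-up timepoints per typical mitral regurgitation intervention clinical studies". Follow-up visits are at 30 days and 1, 2 and 3 years (Protocol 3 and 5.5).

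On method, SAP 2.3.2 says only this: "The analyses for the other endpoints will be performed using the methods described in Section 2.2 for the ITT population". For continuous data, SAP 2.2.1 gives summaries per variable and, as its only contrast, "Differences between the two groups, where specified, will be summarized with the differences of the two means". For categorical data, SAP 2.2.2 gives counts and percentages and "Differences between the two groups, when specified, will be summarized with the difference in percent". On missing data, SAP 2.6 says: "All analyses will be based on available data. Missing data will not be imputed". The one fallback is the 30-day echocardiogram for APS.

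No section defines a change from baseline in the same patients, a shift table, a repeated-measures model or a category for death at a visit. The SAP reference list includes sources on the paired t test, McNemar's test and Bowker's test, but no analysis section calls on them.

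**The concern.** The surveillance is meant to inform on efficacy as well as safety (Protocol 1, SAP 1.2), and it feeds annual reports and a re-examination report (Protocol 3). A reader of those reports will set the baseline summary beside the 1-, 2- and 3-year summaries. Under the available-data rule these describe different sets of patients: everyone measured at baseline, then only those alive and measured at the visit.

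There are three routes of loss that need not be random:
- **Death.** Protocol 5.1 records surgical risk: "Subject is deemed difficult for mitral valve surgery due to either STS surgical mortality risk for mitral valve replacement", with a threshold of 8% or a listed factor such as functional MR with LVEF below 40%.
- **Non-attendance.** Follow-up data are collected by visit, so patients too ill to attend contribute nothing.
- **Failed attempts.** Under Protocol 2.2, patients treated otherwise after a failed attempt generally need no follow-up, yet under SAP 2.1.1 they stay in the analysis population.

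The SAP handles both problems elsewhere. Death or mitral surgery before discharge counts against APS (SAP 1.4.1), and heart failure hospitalisation gets a pre/post model with each patient's own data (SAP 2.2.4). Neither protection reaches the 1- to 3-year NYHA, LV and MR summaries.

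**Working it through.** The plan has no figure on this point. Its one computed design figure, the 5.4% upper limit for SLDA with 250 patients (Protocol 7.2), reproduces as 5.45% (one-sided 95% Clopper-Pearson with 0.03 × 250 = 7.5 events). It has no bearing here.

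**Inputs.** The documents give no mortality, dropout or baseline NYHA distribution, so all of these are assumptions:
- q, the baseline share in NYHA III/IV: 40% or 60%
- m, the share dead or not assessed at 3 years: 20%, 30% or 40%
- RR, the risk of loss in III/IV relative to I/II: 1, 1.5, 2 or 3
- true change in every patient: none

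**Formulas.**
- Loss in I/II: a = m / (q × RR + 1 − q)
- Loss in III/IV: RR × a
- Observed 3-year share in I/II: (1 − q)(1 − a) / (1 − m)
- Apparent gain: observed share minus (1 − q)

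**Worked case, q = 0.6, m = 0.3, RR = 2.**
1. a = 0.3 / (1.2 + 0.4) = 0.1875; loss in III/IV = 0.375.
2. Observed share = 0.4 × 0.8125 / 0.7 = 0.325 / 0.7 = 46.4%.
3. Apparent gain = 46.4 − 40.0 = 6.4 points, with no patient changed.
4. Same patients at both visits: 46.4% and 46.4%, a change of 0.
5. Over all patients: 32.5% assessed and in I/II, 0.6 × 0.625 = 37.5% assessed and in III/IV, 30.0% dead or not assessed.

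**Range: apparent gain in NYHA I/II, percentage points.**

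| Baseline I/II | Loss | RR 1 | RR 1.5 | RR 2 | RR 3 |
|---|---|---|---|---|---|
| 60% | 20% | 0 | 2.5 | 4.3 | 6.7 |
| 60% | 30% | 0 | 4.3 | 7.3 | 11.4 |
| 60% | 40% | 0 | 6.7 | 11.4 | 17.8 |
| 40% | 20% | 0 | 2.3 | 3.8 | 5.5 |
| 40% | 30% | 0 | 4.0 | 6.4 | 9.4 |
| 40% | 40% | 0 | 6.2 | 10.0 | 14.5 |

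**LV measures.** The mean in those still measured is (overall mean − m × mean in those lost) / (1 − m). Assume a baseline LVEDV of 150 mL overall and 165 mL in those lost, with no true change:
- m = 0.2: (150 − 33) / 0.8 = 146.25 mL, a fall of 3.8 mL
- m = 0.3: (150 − 49.5) / 0.7 = 143.57 mL, a fall of 6.4 mL
- m = 0.4: (150 − 66) / 0.6 = 140.0 mL, a fall of 10.0 mL

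**MR grade.** Registration is for 3+ and 4+ MR (Protocol 2.1), so the baseline share at 2+ or less is essentially zero. If no patient changed, it would be zero among survivors too, whatever the loss. From discharge onward the share is no longer zero. If patients left with more than 2+ are lost more often, the share at 2+ or less among those still measured rises by the same mechanism. The documents give no discharge distribution, so no size is put on this.

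**The case against.** The strongest reply is that attrition is not hidden. Protocol 7.3 names Kaplan-Meier analysis for all-cause mortality, SAP 2.2.3 sets out the method, and SAP 3.3 tabulates deaths, withdrawals and losses at every scheduled visit. Numbers of observations accompany means, and patient counts accompany percentages. The study is descriptive with no hypothesis tests, these are secondary measures, and the SAP leaves paired summaries unspecified without excluding them. All of this stands, and it limits the point to interpretation: no error rate, primary endpoint or sample size is touched. But the separate tables show how many patients were lost, not their baseline NYHA class or ventricular size, so a reader cannot correct the visit summaries from them. In a descriptive study the summary is the result.

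Four stronger readings are tempting, and the documents do not support them.
- **The independent-sample interval is misused.** SAP 2.2.2 names "the Newcombe³ score 95% confidence interval for the difference of two percentages", and its source concerns independent proportions. But two-group differences apply only where specified, and the comparison specified is the first 250 against the second 250 patients (SAP 1.4.3 and 2.10), which are independent groups. No unpaired contrast of visits is planned.
- **Patients with later mitral surgery or a repeat clip are counted at their new MR grade.** The SAP is silent on this. That is a gap to close, not a stated rule.
- **The population is high-risk by entry criterion.** The surgical-risk item in Protocol 5.1 is recorded at baseline; it is not a registration criterion in Protocol 2.1 or 2.2. It also concerns surgical mortality, not 3-year mortality after this procedure.
- **The fall in MR from baseline could be an artefact of loss.** Entry at 3+ or 4+ rules this out for MR of 2+ or less.

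**Conclusion.** The point holds as a gap in specification that is worth closing. Followed as written, the plan yields NYHA and LV summaries on shrinking sets of survivors who attend, and these can show improvement that no patient had. The size is zero if loss is unrelated to status, and about 2 to 18 points in NYHA I/II under 20-40% loss, 40-60% of patients in III/IV at baseline and a relative risk of loss of 1.5 to 3. All of these values are assumed. A reader might infer that improvement will appear for this reason; the documents support only that it can, because they give no mortality or loss rates. For MR grade, the exposed claim is durability after discharge.

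**What to change.** Amend SAP 2.3.2 to specify two summaries.

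(a) **Same patients at both visits.** For LV measures, the mean paired change from baseline with its 95% CI. For NYHA, a shift table from baseline and an interval for paired proportions for class I/II. For MR, a shift table from discharge to each later visit; a paired interval against baseline for 2+ or less would be close to degenerate.

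(b) **All registered patients due at the visit.** One table each for NYHA class and MR grade, in mutually exclusive categories assigned in this order:
1. dead
2. alive after mitral surgery or repeat MitraClip since the index procedure
3. not assessed, with failed attempts for which Protocol 2.2 requires no follow-up on their own line
4. otherwise, the NYHA class or MR grade

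The stated order settles overlaps such as a repeat clip followed by death. Not assessed stays a category of its own and is not counted as failure, so nothing is imputed and SAP 2.6 is respected. Durability statements should rest on (b), because (a) removes the change in patient mix but still describes only those assessed at both visits.

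The cost is SAP wording and two summaries per endpoint. NYHA class and TTE are already scheduled, and deaths and reinterventions needing hospitalisation are already reportable as serious adverse events (Protocol 5.9). The downside for the sponsor is that the 3-year percentages over all patients will be lower than those on available data.

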2.7 Subgroups for Analysis

Subgroup analysis may be performed as required to evaluate the safety and efficacy of MitraClip.

2.8 Poolability Analysis

Poolability analysis will be performed as required to evaluate the primary endpoints of MitraClip across different sites. Center effect on the primary endpoint may be investigated based on Fisher's exact test. For the analysis of center effect, data from smaller sites may be combined for the analysis. If there is evidence of inconsistency in the primary endpoints across sites, patient's demographics, baseline clinical and echocardiogram characteristics may be examined.

2.9 Adjustments for Covariates

Unless otherwise specified, no adjustments for covariates will be made for any of the variables in the analyses.

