1.4.3 Exploratory Endpoint(s)

The primary endpoints will be compared between the first 250 registered patients to the second 250 registered patients (or a 2-year registration period, whichever comes first), in order to evaluate the learning curve of the MitraClip procedure.

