2.10 Exploratory Analysis

The safety and efficacy outcomes in the first 250 registered patients will be compared to that of the second 250 registered patients (or end of the 2-year enrollment period, whichever occurs first) to evaluate the learning curve of the MitraClip procedure. The analyses will be performed using the methods described in Section 2.2 for the ITT population.

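### The first-250 versus second-250 learning-curve comparison (SAP 2.10) is planned only as a crude difference, with no baseline table by cohort, so any change in case mix would be mixed with experience

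*SAP*

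**What the plan says.** SAP 1.4.3 states: "The primary endpoints will be compared between the first 250 registered patients to the second 250 registered patients", with the purpose given as "in order to evaluate the learning curve of the MitraClip procedure". Those endpoints are single leaflet device attachment (SLDA) at 30 days and APS at discharge. SAP 2.10 extends the comparison to safety and efficacy outcomes generally, for the same purpose. The second cohort ends early if the 2-year registration period ends first.

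On method, SAP 2.10 says: "The analyses will be performed using the methods described in Section 2.2 for the ITT population". In that section, two-group differences in binary outcomes "will be summarized with the difference in percent and the Newcombe³ score 95% confidence interval for the difference of two percentages" (SAP 2.2.2), and those in continuous outcomes "will be summarized with the differences of the two means, and 95% confidence intervals for the difference between the means" (SAP 2.2.1). Neither is adjusted or stratified.

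SAP 2.9 adds: "Unless otherwise specified, no adjustments for covariates will be made for any of the variables in the analyses". Neither SAP 1.4.3 nor SAP 2.10 specifies otherwise.

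Three other sections bear on the point, but none is tied to the two cohorts:
- SAP 3.1 summarises baseline variables for the ITT population and does not mention a split by cohort.
- SAP 2.8 allows baseline characteristics to be examined, but only if the primary endpoints are inconsistent across sites.
- SAP 2.7 allows subgroup analyses as required and names none.

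**The concern.** The cohorts are defined by registration order and are not randomised. The surveillance takes consecutive patients over about 2 years, with functional or degenerative MR, grade 3+ or 4+, and no stated LVEF limit (Protocol 2.1, 3 and 5.1). If sites treat a different mix later in registration, the crude difference in APS or SLDA reflects both the mix and operator experience. A move towards easier cases could look like learning where there is none. A move towards harder cases could hide real learning.

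The plan as written gives the reader no way to tell these apart, and without a baseline table by cohort the reader could not even see whether the mix had changed. An experience-based reading is foreseeable, because Protocol 7.2 already sets the lower SLDA rates of later trials beside investigators' growing experience.

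**Working it through.** **Plan's own figure.** The documents give no precision figure for this comparison. The only one nearby is in Protocol 7.2: a one-sided 95% upper limit of 5.4% for an SLDA rate of 3% with n = 250. The Clopper-Pearson limit with x = 0.03 × 250 = 7.5 is the 0.95 quantile of Beta(8.5, 242.5), which is 5.45%. That agrees to within 0.05 points, and nothing below depends on it.

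**Inputs.** The documents supply 250 patients per cohort (SAP 2.10) and the Newcombe 95% interval (SAP 2.2.2). They give no APS by patient type and no case mix over time, so these are assumed:
- APS of 95% in easier cases and 80% or 85% in harder cases, the same in both cohorts (no learning).
- Share of harder cases falling from s1 in the first cohort to s2 in the second.

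**Formulas.**
- Cohort APS = 0.95 × (1 − s) + p_hard × s.
- Apparent change = (0.95 − p_hard) × (s1 − s2).
- Newcombe limits, with d = p2 − p1 and Wilson limits (l, u) for each cohort: lower = d − √[(p2 − l2)² + (u1 − p1)²]; upper = d + √[(u2 − p2)² + (p1 − l1)²].
- Chance that the interval excludes zero: the sum of the binomial probabilities of all pairs of counts (0 to 250 in each cohort) whose Newcombe interval excludes zero.

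**Results for APS.** The interval is evaluated at the expected proportions.

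| Harder share | p_hard | First → second | Apparent change (Newcombe 95% CI), points | Chance of excluding zero |
|---|---|---|---|---|
| 50% → 40% | 85% | 90.0% → 91.0% | +1.0 (−4.24 to +6.25) | 6% |
| 50% → 40% | 80% | 87.5% → 89.0% | +1.5 (−4.21 to +7.22) | 8% |
| 50% → 30% | 85% | 90.0% → 92.0% | +2.0 (−3.11 to +7.15) | 12% |
| 50% → 30% | 80% | 87.5% → 90.5% | +3.0 (−2.55 to +8.58) | 19% |
| 60% → 20% | 85% | 89.0% → 93.0% | +4.0 (−1.08 to +9.16) | 34% |
| 60% → 20% | 80% | 86.0% → 92.0% | +6.0 (+0.49 to +11.58) | 57% |

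Each chance is a probability within its own scenario. With no shift it is about 5%. A 40-point fall placed at 70% → 30% gives the same apparent changes with slightly lower chances (31% and 53%). In every row the change within each stratum is 0, so a difference stratified on the right variable has expectation 0.

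**SLDA.** Take stratum rates of 6.3% and 1.8%, which are two values from Protocol Table 1 used here only as assumed strata, and a harder share falling from 50% to 30%:
- First cohort: 0.5 × 6.3 + 0.5 × 1.8 = 4.05%.
- Second cohort: 0.3 × 6.3 + 0.7 × 1.8 = 3.15%.
- Apparent change: −0.90 points (Newcombe −4.47 to +2.59).

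At an SLDA rate of 3%, 0.03 × 500 = 15 events are expected in both cohorts together, too few to support a model with several covariates.

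**The case against.** **The stakes are low.** The comparison stands only under exploratory headings. Protocol 7.3 plans no hypothesis tests, and no decision rule rests on this contrast. Whether a descriptive interval excludes zero is a test-like yardstick that the plan does not use. This stands and limits the weight of the point.

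**The harm is conditional.** The documents do not show that case mix will shift, or that APS differs by 10–15 points between patient types. With a 10-point shift the distortion is 1.0–1.5 points and the chance of excluding zero barely exceeds 5%. The second cohort may also fall short of 250, which would widen the interval. All of this stands.

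**Adjustment may remove part of the target.** Better patient selection can itself be learning. A model also does not isolate learning if sites that start later differ in both mix and experience. Because SAP 2.6 allows no imputation, a model with LVEF would drop patients with missing values. These points stand. They argue for showing raw and adjusted figures together, and for giving the raw figure in the same patients.

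**Stronger readings that the text does not support.** A reader might infer that SAP 2.9 forbids adjustment. It does not: it is a default with an exception clause, which SAP 2.10 simply does not use. A reader might also infer that the SAP commits to calling any difference learning. It names learning as the purpose of the comparison but does not say how a difference will be interpreted.

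What does not stand is that SAP 2.7 or 2.8 already covers the gap. Both are optional, and neither is linked to the two cohorts.

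**Conclusion.** The point holds as a conditional weakness of one exploratory analysis. As written, the plan cannot separate a change in case mix from a change with experience, because the comparison is crude and baseline variables are not planned by cohort. Under the assumed rates and no learning, the apparent APS change runs from 1.0 to 6.0 points for falls of 10 to 40 points in the harder share. The chance that the interval excludes zero runs from 6% to 57%. The upper end needs both the largest shift and the widest gap between strata. These figures rest on 250 patients per cohort and on stratum rates that the documents do not give.

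It would be wrong to conclude that a spurious learning effect is expected, or that the primary SLDA and APS estimates are biased. Those are estimated in the whole ITT population (SAP 2.3.1) and are unaffected. The change is worth making because it is cheap and uses baseline data already collected.

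**What to change.** Add one paragraph to SAP 2.10, worded as a stated exception to SAP 2.9:

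1. Show the SAP 3.1 baseline variables by cohort.
2. For APS, report beside the raw Newcombe difference a standardised risk difference with 95% CI from a logistic regression on cohort, MR etiology, baseline MR grade (3+ or 4+) and LVEF. Give the raw difference in the same complete-case patients as well. Label the raw figure 'total change' and the adjusted figure 'change at the same case mix'.
3. For SLDA, keep the raw difference as the main figure, with at most a difference stratified by etiology as supportive, because few events are expected.

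The cost is one paragraph, one table split and one extra model. No new data are needed, since Protocol 5.1 already collects etiology, MR severity and LVEF. The downsides are the loss of patients with missing covariates from the adjusted figure, and the possible removal of learning that acts through patient selection. Naming the covariates before the analysis also avoids choosing them after the results are seen.
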